4.4 End of Study Definition

A participant has completed the study if he/she has completed all study parts, including all scheduled procedures (including survival follow-up).

The end of the study is defined as the date of study intervention discontinuation by all participants (due to either disease progression, undue toxicity, or withdrawal, and, therefore, are not likely to benefit from the study intervention any longer) and two thirds of the participants have died or were followed up for at least 3 years, whatever occurs first. After the end of the study a final analysis, including an analysis of efficacy and safety, will be conducted in all participants.

5 Study Population

The criteria in Sections [5.1](#) (Inclusion Criteria) and [5.2](#) (Exclusion Criteria) are designed to enroll only participants, who are appropriate for the study; thereby, ensuring the study fulfills its objectives. All relevant medical and nonmedical conditions should be taken into consideration when deciding whether a participant is suitable for this study.

Prospective approval of protocol deviations to inclusion and exclusion criteria, also known as protocol waivers or exemptions, is not permitted.

Before performing any study assessments that are not part of the participant's routine medical care, the Investigator will confirm that the participant has provided written informed consent, as indicated in [Appendix 2](#) (Study Governance).

5.1 Inclusion Criteria

Participants are eligible to be included in the study only if all the following criteria apply:

Age

1. Are \geq 18 years of age (or having reached the age of majority according to local laws and regulations, if the age of majority is $>$ 18 years of age [ie, \geq 20 years of age in Japan]), at the time of signing the informed consent.

Type of Participant and Disease Characteristics

2. Are participants with the following:
 - a) Locally advanced or metastatic NSCLC histology (confirmed by either histology or cytology) with documented activating EGFR mutation.
 - b) Presence of at least 1 independently verified measurable lesion in accordance with RECIST Version 1.1, that can be accurately assessed at Baseline with ≥ 10 mm in the longest diameter (except lymph nodes which must have short axis ≥ 15 mm) with computed tomography (CT) or magnetic resonance imaging (MRI), which is suitable for accurate repeated measurements and that preferably was not previously irradiated or biopsied.
 - c) Eastern Cooperative Oncology Group (ECOG) performance status of 0 or 1 and a minimum life expectancy of 12 weeks.
 - d) Acquired resistance on previous first-line osimertinib. Participants must meet both of the following 2 criteria:
 - Radiological documentation of disease progression on first-line osimertinib.
 - Objective clinical benefit documented during previous osimertinib therapy, defined by either partial or complete radiological response, or durable stable disease (SD) (SD should last > 6 months) after initiation of osimertinib.
 - e) Have received only first-line osimertinib as a prior line of therapy in the noncurative advanced or metastatic NSCLC setting.
 - f) MET amplification as determined by either FISH testing (central or local) on tumor tissue (TBx) or central blood-based next generation sequencing (LBx). Tumor and blood samples must be collected following progression on prior first-line osimertinib at Prescreening.
 - Submission of tumor tissue and blood sample obtained after progression on first-line osimertinib, is mandatory for all patients for MET amplification testing.
 - Submission of tumor tissue during Prescreening or Screening is mandatory for patients with tumor tissue tested by local FISH, to confirm MET amplification status. Central confirmation is not mandated prior to the start of study treatment.

Weight

Not applicable.

Sex

3. Are male or female

- a) Female participants:

Are **not** pregnant or breastfeeding, and at least 1 of the following conditions applies:

- Not a woman of childbearing potential (WOCBP)

OR

- If a WOCBP, use a highly effective contraceptive method (ie, with a failure rate of <1% per year), preferably with low user dependency, as described in [Appendix 3](#) for the following time periods:
 - Before the first dose of the study intervention(s), if using hormonal contraception:

1. has completed at least one 4-week cycle of an oral contraception pill and either had or has begun her menses

OR

2. Has used a depot contraceptive or extended-cycle oral contraceptive for least 28 days and has a documented negative pregnancy test using a highly sensitive assay.

AND

- A barrier method, as described in [Appendix 3](#).

- During the intervention period
- After the study intervention period (ie, after the last dose of study intervention is administered) for at least 2 months after the last dose of study intervention and agree not to donate eggs (ova, oocytes) for reproduction during this period.

The Investigator evaluates the effectiveness of the contraceptive method in relationship to the first dose of study intervention.

- Have a negative serum pregnancy test, as required by local regulations, within 28 days before the first dose of study intervention.
- Additional requirements for pregnancy testing during and after study intervention are in Section [8.2.4](#).

The Investigator reviews the medical history, menstrual history, and recent sexual activity to decrease the risk for inclusion of a female with an early undetected pregnancy.

b) Male participants:

Agree to the following during the study intervention period and for at least 4 months after the last dose of study intervention:

- Refrain from donating sperm

PLUS, either:

- Abstain from intercourse with a WOCBP

OR

- Use a male condom: when having sexual intercourse with a WOCBP, who is **not** currently pregnant, and advise her to use a highly effective contraceptive method with a failure rate of < 1% per year, as described in [Appendix 3](#), since a condom may break or leak.

Informed Consent

4. Can give signed informed consent, as indicated in [Appendix 2](#) (Study Governance), which includes compliance with the requirements and restrictions listed in the informed consent form (ICF) and this protocol.

5.2 Exclusion Criteria

Participants are excluded from the study if any of the following criteria apply:

Medical Conditions

1. Spinal cord compression or brain metastasis unless asymptomatic, stable or not requiring steroids for at least 2 weeks prior to start of study intervention. Prior radiotherapy or surgery for brain metastases such as stereotactic radiosurgery/gamma knife must have been completed \geq 2 weeks, all others \geq 4 weeks prior to start of therapy. Participants with leptomeningeal disease are ineligible.
2. Any unresolved toxicity Grade 2 or more according to NCI-CTCAE version 5, from previous anticancer therapy with the exception of alopecia.
3. Need for transfusion within 14 days prior to the first dose of study intervention.
4. Participants who have brain metastasis as the only measurable lesion
5. Inadequate hematological function:
 - Hemoglobin < 8.5 g/dL
 - Neutrophils < 1.5×10^9 /L
 - Platelets < 100×10^9 /L.
6. Inadequate liver function:
 - Total bilirubin > $1.5 \times$ ULN
 - AST/ALT/ALP > $3 \times$ ULN
 - For participants with liver metastases:
 - i. Total bilirubin > $1.5 \times$ ULN
 - ii. AST/ALT/ALP > $5 \times$ ULN
 - iii. For participants with bone metastases: ALP > $5 \times$ ULN.

7. Inadequate renal function:

- Renal impairment as evidenced by serum creatinine $\geq 1.5 \times$ ULN, or creatinine clearance (CrCl) < 30 mL/min calculated by the Cockcroft-Gault formula (24-hour CrCl might be requested by the Investigator for confirmation, if calculated CrCl is < 50 mL/min. In such case, participants with 24-hour CrCl < 30 mL/min should be excluded).

$$\text{CrCl (mL/min)} = \frac{[(140 - \text{age(year)}) \times \text{weight(kg)}]}{72 \times \text{serum creatinine (mg/dL)}} \quad \{\times 0.85 \text{ for females}\}$$

8. History of ILD or interstitial pneumonitis including radiation pneumonitis that required steroid treatment.

9. Impaired cardiac function:

- Left ventricular ejection fraction $< 45\%$ defined by echocardiography
- Grade 4 arrhythmia (NCI-CTCAE v5.0)
- Unstable angina pectoris
- Congestive Heart Failure New York Heart Association III and IV
- Myocardial infarction, stroke, or transient ischemic attack within the last 6 months prior to study entry.

10. Corrected QT interval by Fredericia (QTcF) > 470 ms for women and > 450 ms for men at Screening. Any factors that increase the risk of QTc prolongation or risk of arrhythmic events such as hypokalemia, congenital long QT syndrome, family history of long QT syndrome or unexplained sudden death under 40 years of age in first degree relatives, or any concomitant medication known to prolong the QT interval and cause Torsade de Pointes.

11. Hypertension uncontrolled by standard therapies (not stabilized to $< 150/90$ mmHg).

12. Contraindication to the administration of osimertinib.

13. Medical history of liver fibrosis/cirrhosis.

14. Past or current history of neoplasm other than NSCLC, except for curatively treated non-melanoma skin cancer, in situ carcinoma of the cervix, benign prostate neoplasm/hypertropia, or other cancer curatively treated and with no evidence of disease for at least 5 years.

15. Medical history of difficulty swallowing, malabsorption, or other chronic gastrointestinal disease, or conditions that may hamper compliance and/or absorption of the tested product.

16. Major surgery within 28 days prior to Day 1 of study intervention.

17. Known human immunodeficiency virus positivity.

18. Known hypersensitivity to any of the study intervention ingredients.

Prior/Concomitant Therapy

19. Prior treatment with other agents targeting the HGF/MET pathway such as crizotinib, capmatinib, savolitinib, foretinib, glesatinib, cabozantinib, merestinib, onartuzumab, rilotumumab, emibetuzumab, and ficolatuzumab.
20. Participants currently receiving (or unable to stop use at least 1 week prior to receiving the first dose of study intervention) medications or herbal supplements known to be potent inducers of CYP3A4.

Prior/Concurrent Clinical Study Experience

21. Participation in another interventional clinical study (except those participants who were solely involved in other studies where the investigational product was osimertinib in the first-line of therapy) within the 30 days prior to randomization/first dose.

Diagnostic Assessments

Not applicable.

Other Exclusions

22. Substance abuse, active infection, or other acute or chronic medical or psychiatric condition or laboratory abnormalities that might increase the risk associated with study participation at the discretion of Investigators.
23. Legal incapacity or limited legal capacity.
24. Any other reason that, in the opinion of the Principal Investigator, precludes the participant from participating in the study.

5.3 Lifestyle Considerations

On days when PK samples are to be drawn, participants should be instructed to attend the study visit in a fasted state (minimum 6 hours fasting; plain water consumption is acceptable), with no breakfast and prior to taking their dose of tepotinib and osimertinib. After a predose PK blood sample is drawn, the assigned dose of tepotinib and osimertinib should be taken after breakfast. No further food should be consumed until 2 hours after the dose (water is allowed).

Participants will abstain from strenuous exercise for 48 hours before each blood collection for clinical laboratory tests.

5.4 Screen Failures

Prescreening

Generally, repeat of Prescreening is not permitted. However, in case of administrative errors or the provided TBx and/or LBx sample cannot be evaluated at the central testing laboratory, the TBx and/or LBx sample may be collected again (but always after progression on first-line osimertinib and before initiation of study intervention) from a participant without obtaining new consent for Prescreening and using the already assigned participant number.

Screening

Generally, individuals who do not meet the criteria for participation in this study (screen failure) may not be rescreened. However, the Sponsor may be re-approached by the Investigator for an individual participant and may grant an exception to repeat screening procedures. This participant must have a confirmed MET amplification as defined in this protocol but may have failed other inclusion or exclusion criteria in the initial screening. In this case, the rescreened participants will be assigned a new participant number.

6 Study Intervention(s)

Study intervention is any investigational intervention(s), marketed product(s), placebo, or medical device(s) intended to be administered to a study participant per the study protocol. In this protocol, this refers to tepotinib and osimertinib combination therapy or tepotinib monotherapy.

Note: Osimertinib is an approved drug (Tagrisso). While this protocol describes the use of osimertinib in this study, more comprehensive information about osimertinib can be found in the prescribing information/SmPC and other reference sources. Investigators are advised to also take this information into account.

6.1 Study Intervention(s) Administration

Study Intervention Name:	Tepotinib and osimertinib combination, or tepotinib monotherapy
Dose Formulation:	Tepotinib: 250 mg tablets. Osimertinib: 80 mg (and 40 mg) tablets.
Unit Dose Strength(s)/Dosage Level(s):	Tepotinib 500 mg (2 tablets of 250 mg) per day, orally, in cycles of 21-day duration. Osimertinib (Tagrisso): 80 mg once daily. A dose reduction to 40 mg once daily is allowed if required based on individual safety and tolerability in line with the prescribing information.
Route of Administration:	Oral with food
Dosing Instructions:	Participants will take tepotinib at the assigned dose together with osimertinib at the approved dose of 80 mg, orally once daily, approximately at the same time (\pm 2 hours), preferentially each morning immediately after food intake with a full glass of water (approximately 200 mL). Participants assigned to the monotherapy tepotinib treatment will take tepotinib at the 500 mg once daily dose (as currently used in the single agent Phase II study). Participants will be instructed to swallow the tablets wholly and to avoid biting or breaking the tablets or attempting to dissolve in water before taking the dose. For comprehensive dosing instructions refer to Section 6.6.
Supplier/Manufacturer:	Tepotinib: manufactured by Merck Healthcare KGaA. Osimertinib: manufactured by AstraZeneca. Tepotinib and osimertinib are to be supplied by Merck Healthcare KGaA.

Packaging and Labeling	A description of pharmaceutical properties and composition of the formulation is provided in the IB for tepotinib and in the SmPC for osimertinib. Each container will be packaged and labeled per all applicable regulatory requirements and Good Manufacturing Practice Guidelines. Tepotinib and osimertinib kits will be supplied in a ready-to-use format for dispensing to the participant. No additional preparation or labeling steps will be required. Additional details of packaging, including quantity per container and anticipated length of supply per container, and labeling of the study interventions will be defined in a separate Pharmacy Manual.
-------------------------------	--

6.2 Study Intervention(s) Preparation, Handling, Storage, and Accountability

The Investigator, institution, or the head of the medical institution (where applicable) is responsible for study intervention accountability, reconciliation, and record maintenance (ie, receipt, reconciliation, and final disposition records).

- Upon receipt of the study intervention(s), the Investigator or designee must confirm appropriate temperature conditions have been maintained during transit and any discrepancies are reported and resolved before use. Also, the responsible person will check for accurate delivery and acknowledge receipt by signing or initialing and dating the appropriate document and returning it to the location specified. A copy will be archived for the Investigator Site File.
- Only participants enrolled in the study may receive study intervention(s) and only authorized site staff may supply it. All study intervention(s) must be stored in a secure, environmentally-controlled, and monitored (manual or automated) area, in accordance with the labeled storage conditions, and with access limited to the Investigator and authorized site staff. Any deviations from the recommended storage conditions (refer to the Pharmacy Manual for details) should be immediately reported to the Sponsor, and the study interventions should not be used until authorization has been received from the Sponsor. Tepotinib and osimertinib must not be used for any purpose other than the study. For details regarding special handling instructions of the study interventions refer to the Pharmacy Manual and the osimertinib prescribing instructions.
- Dispensing will be recorded on the appropriate accountability forms so that accurate records will be available for verification at each monitoring visit.
 - Study intervention(s) accountability records at the study site will include the following:
 - Confirmation of receipt, in good condition and in the defined temperature range.
 - The inventory provided for the clinical study and prepared at the site.
 - The dose(s) each participant used during the study.
 - The disposition (including return, if applicable) of any unused study intervention(s).
 - Dates, quantities, batch numbers, container numbers, expiry dates, and the participant numbers.

- The Investigator site will maintain records, which adequately documents that participants were provided the doses specified in this protocol, and all study intervention(s) provided were fully reconciled.
- Unused study intervention(s) must not be discarded or used for any purpose other than the present study. No study intervention that is dispensed to a participant may be re-dispensed to a different participant.
- A Study Monitor will periodically collect the study intervention(s) accountability forms.
- Further guidance and information for the final disposition of unused study intervention(s) are provided in the Operations Manual.
- The administration of tepotinib or osimertinib to participants who have not been enrolled into the study is not covered by the study insurance.
- Disposal of study intervention should be according to local regulations and institutional guidelines.

6.3 Measures to Minimize Bias: Study Intervention Assignment and Blinding

This study is performed two-arm, open-label. Once the participant meets all the inclusion and none of the exclusion criteria, the Investigator or delegate will request the study treatment assignment using the Interactive Voice Response System (IVRS). Eligible participants with MET amplification identified centrally or locally by FISH (TBx) will be randomized at a 2:1 ratio to either combination therapy with tepotinib and osimertinib or tepotinib monotherapy. Participants in the Republic of Korea will not undergo randomization but will be assigned exclusively to the combination of tepotinib plus osimertinib, and therefore will not be treated with tepotinib monotherapy. The randomization is implemented in order to assure an objective assignment to the combination and monotherapy to avoid any influence of participant's characteristics on the decision for treatment. The assignment to the two arms will continue until 12 participants with centrally confirmed (FISH testing) MET amplification are included in the monotherapy arm. Afterwards all enrolled participants will receive the combination treatment.

Approximately 20 participants with MET amplification identified by central blood-based next generation sequencing (LBx) only are expected to be assigned to the combination of tepotinib plus osimertinib.

An IRC is implemented to strengthen objectivity and consistency in the evaluation of the primary endpoint.

In addition, an Independent Data Monitoring Committee (IDMC) of external experts will perform periodic reviews and assess benefit risk of the overall study including all participants. This independent review is considered to also improve the overall quality of the data.

Participant numbers will be assigned in the appropriate format and will reflect study number, site number and participant identification. Participant numbers will not be reassigned to other participants or reused in this study. If a participant is replaced, the replacement will be enrolled

with a unique participant number. If a participant is allowed to be re-screened for the study, a new participant number will have to be assigned.

6.4 Study Intervention Compliance

Acceptable compliance for this study will be defined in the Monitoring Plan.

Each participant will record on a diary card the number of tablets and dosage of tepotinib/osimertinib taken daily including actual time of intake. This diary card will be returned to the Investigator site at each visit.

Participants may be withdrawn from the study intervention in the event of noncompliance that is deemed by the Investigator or Sponsor to compromise participant safety or study integrity (refer to Section 7.1 and Section 8.4).

Participants should be instructed to bring with them to each visit both opened and unopened tepotinib/osimertinib packages, in order to allow the assessment of compliance with study intervention. Tepotinib/osimertinib administration must be recorded in the electronic Case Report Form (eCRF), as applicable.

6.5 Concomitant Therapy

Record in the eCRF all concomitant therapies (eg, medicines or nondrug interventions) used from the time the participant signs the informed consent until completion of the study, including any changes. For prescription and over-the-counter medicines, vaccines, vitamins, and herbal supplements, record the name, reason for use, dates administered, and dosing information.

Contact the Medical Monitor for any questions on concomitant or prior therapy.

6.5.1 Rescue Medicine

The study will be performed at a clinical research site with personnel trained in basic or immediate life support. Equipment and other agents (epinephrine and prednisolone equivalents, etc.) will be available at the site in case of allergic reactions.

6.5.2 Permitted Medicines

Any medicines that are considered necessary to protect the participant's welfare in emergencies may be given at the Investigator's discretion, regardless if it results in a protocol deviation.

The only permitted medications are the following, but restrictions may apply:

- Concomitant medications that have a narrow therapeutic window and are known to be transported by P-gp (eg, rivaroxaban, apixaban, ranolazine, talinolol, and digoxin), BCRP (eg, rosuvastatin), OCT2, MATE1, and MATE2 (eg, dofetilide and metformin), OATP1B1 and OCT1 are permitted. However, cautionary use and close monitoring of signs of changed tolerability due to potentially increased exposure is advised.

- Refer to Appendix 3 for contraceptive methods for WOCBP and female partners with childbearing potential of male study participants. Accordingly, WOCBP enrolled in the study are to use effective contraception during study intervention and for 2 months after final dose. Males and their female partners are to use effective contraception for 4 months after final dose.
- Supportive treatment, eg, bisphosphonates, agents for improving appetite, if initiated prior to study entry can continue. Change in dose/schedule on study is discouraged.
- Symptomatic treatment of brain metastasis with anticonvulsants known to have a reduced risk for drug interactions such as lamotrigine, levetiracetam, pregabalin, or valproic acid.

The Investigator will record all concomitant medications/procedures taken by the participant during the study, from the date of signature of main informed consent, in the appropriate section of the eCRF.

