addition, dedicated exclusion criteria related to available safety and tolerability information for tepotinib and osimertinib have been introduced in the protocol. Due to the sensitivity of osimertinib to an increase in CYP3A4 activity, strong inducers of CYP3A4 are prohibited. Furthermore, patients with a history of ILD or interstitial pneumonitis, including radiation pneumonitis that require steroid treatment, are excluded.

Osimertinib may prolong the QTc interval. Participants with abnormalities related to cardiac rhythm, conduction, or electrocardiogram (ECG) morphology, or pre-existing QTc risks will therefore be excluded, and the ECG and plasma electrolyte concentrations will be monitored periodically throughout the study. In addition, conditions that can affect left ventricular ejection fraction will be excluded, and echocardiography will be performed at enrollment, end of treatment (EoT), and any time in case of related symptoms in the discretion of the Investigator.

Promising signals for the clinical activity of combinations of EGFR TKIs and MET inhibitors in NSCLC have been observed in clinical studies. In addition, both tepotinib in combination with the EGFR inhibitor gefitinib and osimertinib in combination with the selective MET inhibitor savolitinib have been shown to be safe and well tolerated in clinical studies. Furthermore, the 2 approved EGFR TKIs, ie, gefitinib and osimertinib, have comparable clinical safety profiles. Tepotinib and osimertinib appear not to be prone to drug-drug interactions, and specific exclusion criteria have been defined to reduce the risk for this drug combination. Overall, the available clinical data generated to date indicate a positive benefit risk profile for this new combination and therefore it is considered justifiable to conduct the study, as specified in this protocol.

The study introduces a single agent tepotinib arm to additionally assess the contribution of tepotinib to the osimertinib and tepotinib combination therapy. The 500 mg once daily dose of tepotinib (as used in the ongoing Phase II single agent VISION study) is considered to be safe and in the biologically active range.

More detailed information about the known and expected benefits and risks and reasonably expected AEs of tepotinib and osimertinib may be found in Section 4.2 (Scientific Rationale for Study Design) and the tepotinib IB, as well as the osimertinib prescribing information.

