- Eligible participants with MET amplification identified by FISH (TBx) (central or local) and independent of the MET status by LBx, will be randomly assigned in a ratio of 2:1 to either the combination of tepotinib at a dose defined by the SMC and osimertinib at the recommended daily dose of 80 mg or tepotinib alone at the daily dose of 500 mg (as currently used in the Phase II single agent study) in cycles of 21-day duration (two-arm study). Participants will continue to receive study treatment until disease progression (according to RECIST Version 1.1), death, AE leading to discontinuation, study withdrawal, or consent withdrawal. The randomization to the two arms of the study will continue until 12 participants who are MET amplification positive by centrally confirmed FISH (TBx) are enrolled in the monotherapy arm. After this, all participants will be assigned to the combination of tepotinib plus osimertinib. For participants in the randomized part of the study, verification of disease progression by IRC is required. Participants who are randomized to the tepotinib monotherapy will have the opportunity to switch over to the combination of tepotinib plus osimertinib if they experience disease progression according to RECIST Version 1.1 reported by investigator and verified by IRC. Until progression is verified by IRC and the switch over to the combination of tepotinib plus osimertinib takes place, tepotinib monotherapy can be continued, if judged appropriate by the Investigator. However, if disease progression is not verified by IRC, the participant must discontinue study intervention. Participants who permanently discontinue tepotinib monotherapy due to an AE, withdraw consent, or for any reason other than progressive disease, will not be eligible to switch over to the combination of tepotinib plus osimertinib.

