6.5.3 Prohibited Medicines

Any additional concomitant therapy or procedure that becomes necessary during the study and any change to concomitant drugs must be recorded in the corresponding section of the eCRF, noting the name, dose, duration, and indication of each drug.

The following are not permitted during the study:

- Any other concomitant cancer drug therapy, including chemotherapy, biological therapy, hormonal therapy for anticancer purposes, targeted therapy, or any investigational product other than tepotinib and osimertinib as defined in this protocol
- Any concomitant medication known to prolong the QT interval and cause Torsade de Pointes (refer to [Appendix 8](#))
- Drug(s), for which the package insert/SmPC includes a contraindication for P-gp (eg, dabigatran, aliskiren, colchicine), BCRP, OCT1, OCT2, MATE1, MATE2, or OATP1B1 inhibiting drugs
- Drug(s) that are known to be potent inducers of CYP3A or P-gp and thereby may decrease efficacy of osimertinib and tepotinib, including carbamazepine, phenytoin, rifampicin, and Saint John's wort.

Use of prohibited medicines for any reason must result in withdrawal of the participant from this study. For further details with regard to drug-drug interactions, refer to the tepotinib IB.

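### Protocol Section 6.5.2 names dofetilide as permitted, while Section 6.5.3 and Appendix 8 prohibit it as a Torsade de Pointes drug and require withdrawal

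*Protocol*

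**What the plan says.** Protocol Section 6.5.2 opens its list with "The only permitted medications are the following, but restrictions may apply". The first item covers narrow-therapeutic-window medicines carried by P-gp, BCRP, OCT2, MATE1, MATE2, OATP1B1 or OCT1. For the OCT2/MATE group it reads "eg, dofetilide and metformin), OATP1B1 and OCT1 are permitted". The only condition attached to that item is "However, cautionary use and close monitoring of signs of changed tolerability due to potentially increased exposure is advised".

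Section 6.5.3 then lists what is not permitted during the study, including "Any concomitant medication known to prolong the QT interval and cause Torsade de Pointes", with a reference to Appendix 8. It ends with "Use of prohibited medicines for any reason must result in withdrawal of the participant from this study".

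Appendix 8, Table 6 gives examples of drugs with a known Torsade risk and says that the list is not exhaustive. Dofetilide is one of the entries. In Section 5.2, exclusion criterion 10 counts "any concomitant medication known to prolong the QT interval and cause Torsade de Pointes" among the factors that keep a patient out of the study.

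**The concern.** One drug is both expressly permitted and expressly prohibited, and the prohibition carries mandatory withdrawal. Two things are at stake.

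- **Safety.** Section 2.3 states "Osimertinib may prolong the QTc interval". Participants in the combination arm take osimertinib. Participants randomized to tepotinib alone "will have the opportunity to switch over to the combination of tepotinib plus osimertinib if they experience disease progression" (Section 4.1). By the protocol's own account, dofetilide has a narrow therapeutic window, may reach higher exposure on study treatment, and has a known Torsade risk. Section 6.5.3 exists to prevent that combination.
- **Forced withdrawal.** A site acting in good faith on Section 6.5.2 would trigger withdrawal under Section 6.5.3. Tumor assessments stop at study withdrawal (Section 8.1), so a confirming scan could be lost.

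There is also a smaller effect on data handling. The SAP treats receipt of a prohibited medicine as an important protocol deviation (Section 10.3.1). Both documents drop from the pharmacokinetic (PK) analysis set anyone who received medicines prohibited under protocol Section 6.5 (Protocol 9.3, SAP 8.1). Section 6.5 holds both the permission and the prohibition, so a dofetilide user has no single defined status.

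**Working it through.** The check is mainly a comparison of text, with a short count to show how far the problem extends.

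**Provisions side by side**

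1. Section 6.5.2: dofetilide is named and permitted, with advice to use caution and monitor for increased exposure. The item mentions neither QT nor Torsade and does not refer to Section 6.5.3 or Appendix 8.
2. Section 6.5.3: the Torsade class is not permitted, whatever the reason for use; the consequence is withdrawal.
3. Appendix 8, Table 6: dofetilide is listed by name, so it falls within item 2 without any judgement by the reader.
4. Section 5.2, criterion 10: the same class is excluded at entry.

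Items 2, 3 and 4 are consistent with each other. Item 1 conflicts with all three, so the intended rule is the prohibition and the Section 6.5.2 example is the mistake.

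**How many named drugs are affected**

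Drugs named in Section 6.5.2:
- P-gp: rivaroxaban, apixaban, ranolazine, talinolol, digoxin (5)
- BCRP: rosuvastatin (1)
- OCT2/MATE: dofetilide, metformin (2)
- anticonvulsants: lamotrigine, levetiracetam, pregabalin, valproic acid (4)

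Total: 5 + 1 + 2 + 4 = 12. Table 6 has 59 printed entries. Matching the 12 against the 59 gives one match, dofetilide. The conflict by name is confined to that example.

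**When it can arise**

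Criterion 10 should stop a current user from entering. SAP Section 7 records that global enrollment closed on 8 July 2022 and that enrollment in China continued until 7 November 2022. What remains is a new start of dofetilide during treatment, when Sections 6.5.2 and 6.5.3 are the rules a site would consult.

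**Whether other safeguards prevent it**

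Periodic ECG and electrolyte monitoring (Sections 1.3 and 2.3) and the QTc rules in Table 3 (Section 6.6) detect prolongation or respond to it. Neither stops the drug from being started.

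**Effect on the primary endpoint**

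Section 9.2 plans 80 participants in the primary analysis set for the combination. If one responder were withdrawn before the confirming scan, the ORR would fall by 1/80 = 0.0125, or 1.25 percentage points. This is the weight of one participant; it says nothing about how likely the event is.

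**The case against.** The strongest reply is that the protocol already resolves the conflict. The lead-in to Section 6.5.2 warns that restrictions may apply, and Section 6.5.3 follows directly. One of its items bars drugs whose labels contraindicate inhibitors of largely the same transporters. On that reading, Section 6.5.2 permits a broad class and Section 6.5.3 removes members of it, including those with Torsade risk. This correctly identifies the intended rule, but it does not rescue the example. The permission is for a named drug, the only restriction attached to it is monitoring for exposure, and advice to monitor cannot be read as a ban with mandatory withdrawal. A site that sees the drug named as permitted has little reason to call the Medical Monitor (Section 6.5). The emergency allowance in Section 6.5.2 does not cover routine use.

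Several other points stand in whole or part:

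- The exposed group is very small. Criteria 9 and 10 screen out many patients with arrhythmia or QTc risk, and changes in concomitant medication must be recorded.
- For a monotherapy participant, withdrawal and later exposure to osimertinib are alternatives. If Section 6.5.3 is enforced, there is no switch-over. The two harms should not be added together.
- This is an inconsistency in drafting. No decision on endpoint, estimand or sample size is in question.
- Changing the protocol text is an amendment and needs ethics approval unless there is an immediate hazard (Appendix 2). A site letter can warn sites but cannot edit Section 6.5.2.

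**Conclusion.** The concern holds. Section 6.5.2 is wrong as written: it permits by name a drug that Section 6.5.3, read with Appendix 8, prohibits on pain of withdrawal. The conclusion rests on the protocol text alone and needs no outside pharmacology.

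The problem is one example among 12 named drugs, few participants are likely to be affected, and the primary analysis method does not change. The consequence for any participant who is affected could be serious, because a known Torsade drug would be given alongside one that the protocol says may prolong QTc. The likelihood of a new on-study start cannot be estimated from the documents. The point should be corrected for participant safety and to avoid an unnecessary withdrawal; its effect on the efficacy result is incidental.

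**What to change.** Delete dofetilide from the examples in Section 6.5.2 and keep metformin. After the statement that these medicines are permitted, add: *except medicines prohibited by Section 6.5.3*. Section 6.5.3 already refers to Appendix 8, so no separate mention is needed. The general clause also covers Torsade drugs that Table 6, which is not exhaustive, does not list.

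A clarification letter can tell sites now that Section 6.5.3 governs. The text change can go into the next amendment, with the ethics review that Appendix 2 requires, across the planned 100 to 120 sites. The edit is one deletion and one clause, with no new procedure, data collection or analysis.
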